### 5.6.3 Control Group and Concurrent Treatments

Except for additional treatment during the cooling period, all patients will be treated according to published guidelines for the treatment of acute ischaemic stroke and for secondary prevention. Participation in the trial will therefore not preclude early start of oral acetyl salicylic acid or other treatments. However, patients allocated to cooling will not be able to equally participate in early mobilization exercise during the period of active cooling.

### 5.6.4 Premature Withdrawal

Participation in any research trial is voluntary and therefore the participant or their relative or welfare guardian may wish to withdraw from the trial at any point. If this is the case, it should be made clear on a Premature Withdrawal Form whether any previously collected data may still be used for the analysis and which part of the trial the patient is being withdrawn from;

1. Withdraw entirely – the hypothermia intervention will be safely terminated, no further data will be collected and previous data collected will not be used in the analysis;
2. Withdraw from the intervention – no further data will be collected and the intervention will be safely terminated but data previously collected may be used in the analysis;
3. Withdraw from the intervention but be willing to be followed up;
4. Withdraw from being followed up only (normal care).

If the patient wishes to withdraw from the trial or their relative or welfare guardian wishes to withdraw them, they are free to do so without giving a reason and without the patient's medical care or legal rights being affected. If however the patient is withdrawn from the trial by the doctor in charge of their care on medical grounds, the reason for this withdrawal must be clearly documented in the data collection form and a serious adverse event (SAE) form completed if appropriate.

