### 2.2 ENDPOINTS

#### 2.2.1 Primary Endpoint

- Proportion of patients completing the intervention per protocol.

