#### Feasibility

- Compliance: the proportion of completed interventions (completed = a treatment that is continued until the end of the predefined time period, or earlier in cases where the patient has fully recovered)
- Time to first reaching target oesophageal temperature
- Stability at target temperature (time spent with oesophageal temperature within 0.7°C of target)
- Control of warming (per-protocol rewarming to 36°C taking at least 3 hours 20 minutes (35°C group) or 10 hours (33°C group)).

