### **7.2 PROPOSED ANALYSES**

As this is a pilot phase, we are as interested in whether the treatment can work in theory as whether it will work in practice. We will therefore perform both intention-to-treat and per-protocol analyses, and examine non-compliance to see whether compliance can be improved in the main trial. Statistical analyses will primarily be descriptive, as this is an exploratory study. Continuous outcomes will be presented using means and 95% confidence intervals. Binary outcomes will be presented as proportions with 95% confidence intervals.

If there are no clear problems with the tolerability, feasibility, and safety of cooling to 33°C or of 24 hours cooling, the potentially greater efficacy of cooling to 33°C rather than 35°C and 24 hours rather than 12 hours cooling is likely to lead to consideration of surface cooling to 33°C for 24 hours as the optimum intervention for a phase III trial. However, if there are concerns about tolerability feasibility, and safety of cooling to 33°C and/or of 24 hours cooling, a target temperature of 35°C and/or duration of 12 hours might be selected.

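### Full withdrawal under section 5.6.4 option 1 takes the patient's data out of the analysis, although full withdrawal during cooling is a failure on the primary completion endpoint

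*Protocol*

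**What the plan says.** - **Endpoint.** Protocol 2.2.1 gives the primary endpoint: "Proportion of patients completing the intervention per protocol". Section 3, under Feasibility, defines it: "completed = a treatment that is continued until the end of the predefined time period". Stopping earlier also counts as completed if the patient has fully recovered.
- **Withdrawal.** Section 5.6.4 offers four kinds.
  - Option 1, full withdrawal: cooling is ended and "no further data will be collected and previous data collected will not be used in the analysis".
  - Option 2: "the intervention will be safely terminated but data previously collected may be used in the analysis".
  - Option 3: "Withdraw from the intervention but be willing to be followed up".
  - Option 4 ends follow-up only.
  - If the doctor in charge withdraws a patient on medical grounds, the reason must be documented.
- **Analysis.** Section 7.2 promises "both intention-to-treat and per-protocol analyses, and examine non-compliance". It does not say how a full withdrawal counts in the completion proportion.
- **Numbers.** Sections 4.1 and 5.6.1 give 4 patients to each of four cooling arms and 8 to control.

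**The concern.** The trial asks whether awake patients can get through the cooling. Someone who leaves the trial altogether partway through is direct evidence that they sometimes cannot. Option 1 says that this patient's data are not analysed, so a failure can drop out of the very proportion meant to count it.

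The exclusion depends on the outcome, because withdrawing during cooling is itself non-completion. It may also be uneven between arms: section 5.6.2 staggers the arms partly because long cooling to low temperatures is expected to be uncomfortable. Section 7.2 then says that, if no evident problems with tolerability, feasibility or safety appear, the colder and longer regimen is likely to be considered for phase III. An inflated completion proportion pushes in that direction. Section 3 also plans to pool the results with other European pilots, so the same exclusion could carry over.

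An analysis plan could not easily repair this. Section 5.6.4 governs what the patient agrees to on leaving, and data given up on those terms cannot be brought back afterwards.

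**Working it through.** **The plan's own figures.** 4 arms × 4 + 8 controls = 24. Two blocks of 12 allocated 1:1:1 give 4 per group per block, hence 16 cooled and 8 control. Both agree with the protocol. It gives no expected completion rate and no expected withdrawal rate, so the rates below are assumptions.

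**Status of the patient.** Take a patient randomised to cooling who chooses option 1 before the period ends and has not fully recovered. By the definition in section 3 the intervention is not completed. Intention-to-treat keeps the patient in the denominator as a failure; option 1 as written takes the patient out.

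**Direction.** Let x of n cooled patients complete, and let w of the n − x non-completers leave under option 1.

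- All kept: x/n.
- Option 1 as written: x/(n − w), which is larger than x/n whenever w ≥ 1 and x ≥ 1.
- One completer who withdraws entirely afterwards: (x − 1)/(n − 1), which is smaller than x/n whenever x < n.

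**All 16 cooled patients, assuming 12 complete.** Section 7.2 says "Binary outcomes will be presented as proportions with 95% confidence intervals", so exact (Clopper-Pearson) intervals are shown.

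| Non-completers removed | Proportion | 95% CI |
|---|---|---|
| 0 | 12/16 = 75.0% | 47.6–92.7 |
| 1 | 12/15 = 80.0% | 51.9–95.7 |
| 2 | 12/14 = 85.7% | 57.2–98.2 |
| 3 | 12/13 = 92.3% | 64.0–99.8 |
| 4 | 12/12 = 100% | 73.5–100 |

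In the opposite direction, one completer withdrawing entirely later gives 11/15 = 73.3% (44.9–92.2) in place of 12/16.

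**One arm of 4.**

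| All kept | One removed | Two removed |
|---|---|---|
| 3/4 = 75% (19.4–99.4) | 3/3 = 100% (29.2–100) | – |
| 2/4 = 50% (6.8–93.2) | 2/3 = 66.7% (9.4–99.2) | 2/2 = 100% (15.8–100) |

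**Range over assumed rates.** With true completion p and a share q of non-completers choosing option 1, the ratio of expected counts is p / [p + (1 − p)(1 − q)]. For example, p = 0.75 and q = 0.5 give 0.75 / (0.75 + 0.125) = 0.857.

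| p | q = 0 | q = 0.25 | q = 0.5 | q = 1 |
|---|---|---|---|---|
| 0.90 | 90.0% | 92.3% | 94.7% | 100% |
| 0.75 | 75.0% | 80.0% | 85.7% | 100% |
| 0.50 | 50.0% | 57.1% | 66.7% | 100% |

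**The case against.** Only one of the four options bars use of earlier data. A patient who simply cannot bear the cooling may choose option 2 or 3, or be withdrawn on medical grounds, and all of these remain countable as failures. The allocation is held by the web-based randomisation service (5.6.1), and withdrawals go on a form. If the bare facts of allocation and withdrawal are not part of the data that option 1 removes, the patient can still be scored. The analysis is mainly descriptive, there is no completion threshold, and the intervals above overlap widely.

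Much of this stands. It limits the number of failures at risk and makes the effect conditional. It does not remove the conflict: the text does not say that allocation and withdrawal survive option 1, and the denominator of the primary endpoint should not depend on how one clause is read.

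Two stronger readings are tempting, and the protocol supports neither.

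- A reader might infer that the per-protocol analysis makes completion 100% in every arm. Section 7.2 does not define the per-protocol set or say that completion is calculated in it. That analysis is additional to intention-to-treat and to the examination of non-compliance, so it removes no failure from the endpoint.
- A reader might infer that option 2 is a fault of the same kind because it ends later data collection. It does not affect completion, since data up to that point may be used. It is the participant's choice, and option 3 exists for those willing to be followed.

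**Conclusion.** The point holds in a limited form. Option 1, followed as written, conflicts with the intention-to-treat analysis in 7.2 for patients who withdraw entirely before cooling ends without full recovery, and dropping such patients can only raise a non-zero completion proportion.

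The size depends on how many choose option 1, which the protocol cannot tell us. If nobody does, there is no bias. One such patient can move an arm from 75% to 100%. Across 16 cooled patients with an assumed 12 completing, the reported figure could lie anywhere from 75% to 100%. Full withdrawal after completed cooling has a small effect the other way (75.0% to 73.3%).

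It would be too much to say that the endpoint loses its failures in general. It loses only those non-completers who also refuse any use of their data, and only if the rule reaches the facts of allocation and withdrawal.

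**What to change.** State the following in 5.6.4, on the withdrawal form and in 7.2:

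- Every patient randomised to cooling stays in the denominator for completion.
- Full withdrawal before the end of cooling, without full recovery, counts as not completed. Only two facts are used for this, as consent and ethics approval allow: the allocated arm, and that the patient withdrew before cooling ended.
- The number of full withdrawals is reported by arm.
- The primary completion result is the intention-to-treat one among all patients randomised to cooling. Controls have no cooling to complete and are not in this denominator.

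The cost is wording, with no extra patients or assessments. The downside is that a minimal record is kept for people who asked to leave entirely, so the wording needs ethics approval. The consent pages are not in the text available here and would have to be checked for agreement.

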## **6. DATA COLLECTION**

All patient data will be recorded in the case record file by the local investigator assisted by a trial co-ordinator. Safety and other data from all European pilot studies will be collated in Edinburgh by the Chief Investigator assisted by a trial co-ordinator and a statistician. The following data will be collected:

### **6.0.1 Baseline**

1. Date of birth, sex, date and time of stroke onset
2. Medical history and vascular risk factors
3. Oesophageal, tympanic, and rectal and bladder temperatures where available, blood pressure, and heart rate
4. Pre-stroke scores on the mRS and BI
5. NIHSS
6. Laboratory tests, including full blood count, serum glucose, electrolytes, PTT, aPTT, and C-reactive protein
7. Blood samples for analysis of biomarkers of brain injury and for genetic studies
8. 12-lead electrocardiogram
9. CT or MRI scan of the brain, depending on local preference

### **6.0.2 2-3 hours after randomisation**

1. MRI with structural imaging, diffusion imaging and MR spectroscopy with measurement of brain temperature.

### **6.0.3 Randomisation Through to Day 7 ( $\pm$ 1 day; or discharge, if earlier)**

1. Date and time of randomisation
2. Date and time of start of cooling
3. Level of consciousness, presence of shivering, rectal, bladder, and tympanic temperatures, blood pressure, and heart rate every 15 minutes in the first three hours after start of cooling, every 30 minutes thereafter until 12 hours after start of warming, and every 6 hours until day 7 (or discharge, if earlier)
4. Laboratory tests, including full blood count, serum glucose, electrolytes, PTT, aPTT, C-reactive protein, blood samples for biomarker and genetic studies. 12-lead electrocardiogram 6 and 12 hours after randomisation, and at 48 hours
5. NIHSS at 24 and 48 hours and at 7 days (or discharge, if earlier)
6. mRS and BI at day 7 (or discharge, if earlier)
7. Concurrent medication
8. Neurological and systemic adverse events
9. CT or MRI scan at day 7  $\pm$  2 days

### **6.0.4 1 Month and 3 Months ( $\pm$ 14 days)**

Scores on the mRS, BI and NIHSS. To promote objective outcome assessment, a trial nurse will perform a standardised evaluation of each patient, including functional status, and will include the obtained information in an essay. Based on this essay, the members of the trial

steering committee who are blinded to treatment allocation, will determine the scores on the mRS and BI.

Serious adverse events (definition: see 8.1) during the trial period 7 days (or discharge, if earlier) through 3 months.

## **7. STATISTICS AND DATA ANALYSIS**

### **7.1 SAMPLE SIZE CALCULATION**

This is a pilot phase trial of the safety, feasibility and tolerability of a physical intervention. Cooling of 16 patients will allow us to establish whether these target temperatures are feasible; whether further measures are required to increase the tolerability of the treatment. Comparison with the outcome in 8 untreated patients will allow us to make broad inferences about safety. Combining these data with those from other centres will give us better estimates of safety and will inform the design of and sample size calculations for a large-scale clinical trial.

### **7.2 PROPOSED ANALYSES**

As this is a pilot phase, we are as interested in whether the treatment can work in theory as whether it will work in practice. We will therefore perform both intention-to-treat and per-protocol analyses, and examine non-compliance to see whether compliance can be improved in the main trial. Statistical analyses will primarily be descriptive, as this is an exploratory study. Continuous outcomes will be presented using means and 95% confidence intervals. Binary outcomes will be presented as proportions with 95% confidence intervals.

If there are no clear problems with the tolerability, feasibility, and safety of cooling to 33°C or of 24 hours cooling, the potentially greater efficacy of cooling to 33°C rather than 35°C and 24 hours rather than 12 hours cooling is likely to lead to consideration of surface cooling to 33°C for 24 hours as the optimum intervention for a phase III trial. However, if there are concerns about tolerability feasibility, and safety of cooling to 33°C and/or of 24 hours cooling, a target temperature of 35°C and/or duration of 12 hours might be selected.

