#### 2.2.2 Secondary Endpoints

- Feasibility (recruitment rate; time to target temperature; stability at target; control of temperature during warming period)
- Tolerability (Columbia Shivering Score; patient questionnaire)
- Safety (deaths; adverse events including infections, DVT or coagulopathy; pethidine dose required)
- Oesophageal temperatures compared with tympanic, and bladder and/or rectal where available, at baseline, every 15 minutes in the first three hours after start of cooling and every 30 minutes thereafter until 48 hours after stroke onset
- Penumbra temperature 3 hours after initiation of cooling
- National Institutes of Health Stroke Scale (NIHSS) score, the Barthel Index (BI) and the modified Rankin scale (mRS) at three months
- Infarct volume on CT or MRI 7 days after the induction of hypothermia
- Temperature in ischaemic core, surrounding brain, and contralateral hemisphere determined using MR spectroscopy initiated 2-3 hours after the commencement of cooling
- Feasibility of collecting and processing samples for future biomarker study.

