#### 4. TRIAL POPULATION

##### 4.1 NUMBER OF PARTICIPANTS

A total of 24 patients will be included in Edinburgh. Patients will be randomised to conventional treatment (8 patients) or to one of the following four surface cooling strategies (4 patients each): (A) 35°C maintained for 12 hours; (B) 33°C maintained for 12 hours; (C) 35°C maintained for 24 hours or (D) 33°C maintained for 24 hours.

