### **5.6 RANDOMISATION**

#### **5.6.1 Randomisation**

After written informed consent has been obtained, patients will be randomised to conventional treatment or to one of the following four surface cooling strategies: (A) 35°C maintained for 12 hours; (B) 33°C maintained for 12 hours; (C) 35°C maintained for 24 hours or (D) 33°C maintained for 24 hours, using a length-of-time escalation design (see next paragraph). Randomisation will be stratified for the intention to perform intravenous thrombolysis with rt-PA and for stroke severity (dichotomised between NIHSS scores of 13 and 14). The choice to perform intravenous thrombolysis is left at the discretion of the local investigator. Allocation to treatment will be through a web-based randomisation service hosted at the University of Edinburgh. Each active treatment arm will consist of 4 patients and the control group of 8 patients.

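### Means with 95% CIs for continuous outcomes suit neither a time to target that some patients may never reach nor skewed measures shown in arms of 4

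*Protocol*

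**What the plan says.** Section 7.2 gives two summary rules. The first is "Continuous outcomes will be presented using means and 95% confidence intervals"; the second is "Binary outcomes will be presented as proportions with 95% confidence intervals". Both stand under a general statement: "Statistical analyses will primarily be descriptive, as this is an exploratory study".

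Two kinds of outcome fall under the first rule and matter here:

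- Section 3 (Feasibility) lists "Time to first reaching target oesophageal temperature", and section 2.2.2 also names time to target among the feasibility endpoints.
- Section 2.2.2 lists "Infarct volume on CT or MRI 7 days after the induction of hypothermia", and the pethidine dose required as a safety measure.

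On group sizes, section 5.6.1 says "Each active treatment arm will consist of 4 patients and the control group of 8 patients", and section 4.1 says "A total of 24 patients will be included in Edinburgh". Section 7.1 states the purpose of the numbers: "Cooling of 16 patients will allow us to establish whether these target temperatures are feasible". Section 7.2 goes on to say that feasibility, tolerability and safety will inform the choice of depth and duration of cooling for a phase III trial.

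**The concern.** The first rule is a positive choice of method, not a gap left open, and it applies to time to target and to infarct volume because both are continuous.

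For time to target, a patient who never reaches it has no number to average. The analyst must drop that patient or invent a value. Dropping removes the worst results, so a strategy that fails more often can show a shorter mean time. This is one of the outcomes meant to tell the 35°C and 33°C strategies apart.

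For skewed, non-negative outcomes, a symmetric t-interval on four values can extend below zero, where no volume or dose can lie, and its actual coverage is below 95%. A reader designing the next trial could take a wrong impression of location and spread from such a display.

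**Working it through.** The protocol states no SD, CV, alpha or power, so there is no figure of its own to reproduce beyond 4 × 4 + 8 = 24, which agrees with section 4.1. All probabilities and CVs below are assumptions, shown over a range.

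**1. Time to target**

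*Can non-reaching be foreseen?* Yes, from the protocol's own text. The Summary says that 34°C or below may be poorly tolerated by awake patients. Section 1.2.8 calls surface cooling appropriate in awake patients down to about 35°C. Section 1.2.3 cites 34.5°C as the lowest temperature obtained in awake patients by surface cooling. Two of the four cooling arms aim at 33°C.

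*Would the primary endpoint show it?* Not necessarily. Section 3 defines a completed intervention as one continued to the end of its set period, or stopped early because of full recovery. Section 5.6.2 sets the duration as 12 or 24 hours of active cooling. Neither requires that the target be reached, so a patient cooled for the full period who never reaches 33°C can count as completed.

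*How often would an arm of 4 lack a value?* With chance p per patient of not reaching target, P(at least one of 4) = 1 − (1 − p)⁴:

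- p = 10%: 1 − 0.6561 = 34%
- p = 25%: 1 − 0.3164 = 68%
- p = 50%: 1 − 0.0625 = 94%

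*Direction of the error (invented values).* Times of 2, 3, 8 and 12 h have mean 25/4 = 6.25 h. If the slowest patient never reaches target and is dropped, the mean is 13/3 = 4.33 h. The arm has done worse and looks faster. Pooling arms does not cure this.

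**2. Skewed non-negative outcomes**

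The half-width of the interval is t(0.975, n−1) × SD/√n. The lower limit is negative when the sample SD/mean exceeds √n/t.

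| n | t | half-width | lower limit below 0 if sample CV exceeds |
|---|---|---|---|
| 4 | 3.182 | 3.182/2 = 1.59 SD | 0.63 |
| 8 | 2.365 | 2.365/2.828 = 0.84 SD | 1.20 |
| 16 | 2.131 | 2.131/4 = 0.53 SD | 1.88 |

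Simulated lognormal samples (at least 200,000 per row) gave:

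| n | assumed CV | lower limit below 0 | coverage of nominal 95% |
|---|---|---|---|
| 4 | 0.5 | 12% | 92% |
| 4 | 1.0 | 55% | 86% |
| 4 | 1.3 | 68% | 82% |
| 8 | 0.5 | 0% | 92% |
| 8 | 1.0 | 8% | 87% |
| 16 | 0.5 | 0% | 93% |
| 16 | 1.0 | 0.5% | 89% |

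So negative limits mostly disappear in larger groups, while some under-coverage remains.

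*Example (invented volumes).* 5, 20, 40 and 150 ml have mean 53.75 and SD 65.75. The half-width is 1.591 × 65.75 = 104.6, so the interval runs from −50.9 to 158.4 ml.

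**3. Would a CI for the median do instead?**

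Not at n=4. The widest distribution-free interval, minimum to maximum, covers the median with probability 1 − 2 × (1/2)⁴ = 87.5%. Individual values with median and range are what an arm of 4 can support.

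**The case against.** - **The analyses are descriptive.** This stands. The primary endpoint is a proportion, no formal decision rule uses a mean or its interval, and section 7.2 does not forbid showing medians as well. It limits the point to a minor one.
- **Section 7.2 does not say that intervals are per arm.** This also stands. Section 7.1 speaks of 16 cooled patients against 8 controls, and the 2×2 layout allows groups of 8 by depth or by duration. The n=4 figures therefore apply only if results are shown by arm, which the objective of comparing strategies (section 2.1.1) makes likely but does not fix.
- **The protocol does not say that non-reachers are dropped.** True; handling of such cases may be set out in an SAP. But a mean is the named summary, and it cannot be computed without dropping or imputing these patients. A better summary would have to depart from the sentence.
- **Other outcomes would expose the failures.** Partly. Time spent within 0.7°C of target is defined for every cooled patient and would show many failures. It can still credit a patient who comes within 0.7°C and never reaches target. The primary endpoint is worded in section 2.2.1 as completion per protocol, which might be thought to imply reaching target, but the definition in section 3 rests on duration.
- **The CVs are assumed.** True. At CV 0.5 the effect is small.

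A reader might go further and infer that every outcome that is not binary, including mRS, BI, NIHSS and the shivering score, is to be shown as a mean. The text does not support this. Section 7.2 says continuous, and nothing assigns the ordinal scales to that rule. Their summary is simply not stated, which a protocol may leave to its SAP. Nor are most outcomes unsuited: means are a normal summary for the many temperature measurements.

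**Conclusion.** The concern holds in limited form, as a minor point. The means rule is a poor choice for time to target, where a mean over reachers can favour the arm that fails more often. How likely that is depends on the assumed failure rate: 34% to 94% of arms of 4 would lack at least one value for failure rates of 10% to 50% per patient. The rule is also a poor choice for skewed non-negative measures if they are shown by arm of 4: 12% to 68% of lower limits fall below zero and coverage is 92% to 82% for assumed lognormal CVs of 0.5 to 1.3. It would be wrong to say that the rule always gives impossible intervals. With a sample CV below 0.63 at n=4 the lower limit stays positive, and at CV 1.0 negative limits are rare in groups of 16.

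**What to change.** Amend the one sentence in section 7.2 to say, in substance:

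- Time to target is reported as the proportion of patients reaching target, with a median in which patients who never reach it are kept as not reached and ranked last. In an arm of 4 this median has a value with up to one non-reacher; with two or more, it is reported as not reached.
- Skewed continuous outcomes, such as infarct volume and pethidine dose, are shown in arms of 4 as individual values with median and range.
- Means with 95% CIs are kept for roughly symmetric measures such as temperatures.

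The cost is wording only. No extra data are needed, since oesophageal temperature is already recorded continuously in cooled patients. Keeping non-reachers visible would also help the planned meta-analysis with the other European pilots (section 3).
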